7.4.4 Additional Endpoints

No formal statistical hypothesis will be formulated and tested for the additional endpoints. Additional details are described in section 7.11 in the SAP.

7.4.4.1. Additional Procedural Endpoints

- Total procedure time, PVI time, PF application time and mapping time
- Number of PF applications by left and right PV and by subject
- Total fluoroscopy time
- Total study catheter left atrial dwell time
- Ablation settings used

7.4.4.2. Additional Safety Endpoints

- Occurrence of Serious Adverse Device Effects (SADEs)
- Occurrence of Unanticipated (Serious) Adverse Device Effects (USADEs)
- Occurrence of Serious Adverse Events (SAEs) within 7 days (early-onset), 8-30 days (peri-procedural), and >30 days (late onset) of index ablation procedure
- Occurrence of non-serious adverse events (non-SAEs)

7.4.5 Additional Effectiveness Endpoints

- **Single Procedural Success** is defined as freedom from documented symptomatic atrial arrhythmia (AF, AT or AFL of unknown origin*) episodes based on electrocardiographic data (≥ 30 seconds on arrhythmia monitoring device) during the effectiveness evaluation period (Day 91-Day 365) following a single index ablation procedure. Subjects who had repeat procedure(s) for the study arrhythmia post the index procedure will be deemed failures of this endpoint.
- **Freedom from documented symptomatic atrial arrhythmia (AF, AT or AFL of unknown origin*):** The time to first documented symptomatic atrial arrhythmia (AF, AT or AFL) recurrence based on electrocardiographic data (≥ 30 seconds on arrhythmia monitoring device) during the effectiveness evaluation period (Day 91-Day 365) at 12 months post the index procedure.

Acute procedural failure (i.e., failure to confirm entrance block in all PVs except those that are silent and/or cannot be cannulated post-procedure, use of non-study catheter for PV isolation, and failure to have energy delivery with the study device due to ablation system malfunctions) will also be considered a failure.

- **Freedom from documented (symptomatic and asymptomatic) atrial arrhythmia (AF, AT or AFL of unknown origin*) with additional failure models:** The time to first documented (symptomatic and asymptomatic) atrial arrhythmia (AF, AT or AFL) based on electrocardiographic data (≥ 30 seconds on arrhythmia monitoring device) during the effectiveness evaluation period (Day 91-Day 365). The following criteria will also be deemed failures:
 - Failure to achieve acute procedural success.
 - Taking a new Antiarrhythmic Drug (AAD) (Class I / Class III) for atrial tachyarrhythmia (AF, AT or AFL of unknown origin*) or taking a previously failed Class I/III AAD at a greater than the highest ineffective historical dose for AF/AFL/AT during the effectiveness evaluation period (Day 105* – Day 365).
 - Greater than 1 repeat ablation for AF/AT or AFL of unknown origin* in the blanking period or any repeat ablation for AF/AT or AFL of unknown origin* during the effectiveness evaluation period.

CCI

- **Use of a non-study device** for the purpose of PVI (i.e., touch-up) among all clinically relevant targeted PVs.
- **Acute reconnection** defined as any pulmonary vein reconnection during the index procedure identified by adenosine/isoproterenol challenge among all clinically relevant targeted PVs.
- **Repeat ablation procedures** for left atrial arrhythmia (AF, AT or AFL of unknown origin*) within the 12-month FU period.
- **Quality of Life (QoL)** is defined as the change of QoL assessed by comparing the Atrial Fibrillation Effect on Quality-of-Life (AFEQT™) scores before and at 3, 6 and 12- months after the ablation procedure.
- **Hospitalization for cardiovascular events** through 12 months follow-up compared to 12 months prior to baseline.

CCI

7.5 Analysis of Primary Endpoints

The primary safety and acute effectiveness endpoints will be evaluated based on 3-month follow-up and procedural data respectively. The hypothesis testing of these primary endpoints will be performed once all subjects treated with the OMNYPULSE™ catheter and TRUPULSE™ Generator have completed their 3-month follow-up. The results will be reported in the 3-Month CSR. Additionally, the Final CSR will include descriptive statistics based on the final complete follow-up data, if there is any primary endpoint data change after the database extraction for the 3-Month CSR. The 3-Month CSR will be submitted as a part of the CE mark application dossier.

7.5.1 Primary Safety Endpoint

The primary safety endpoint will be analyzed using the 3-month PAE rate.

Analysis Method:

The primary safety endpoint will be evaluated using an exact test for a binomial proportion at a one-sided significance level of 2.5%. If the upper bound of the exact two-sided 95% confidence interval of the primary safety endpoint rate is less than the performance goal of 12%, the study will be considered to have demonstrated safety. The study has met its primary safety endpoint.

The hypothesis testing will be performed in the mITT analysis set. Subjects with non-missing PAE outcome data will be included in the primary analysis. The number of events, number of subjects who experience PAEs, and percentage of subjects who experience PAEs will be reported, along with the exact two-sided 95% confidence interval.

To investigate the robustness of the analysis result, sensitivity analyses including estimation of the PAE rate in the Safety analysis set, worst-case and best-case scenario analyses, and tipping point analysis will be performed in the Safety and mITT analysis sets. Details are provided in Section 7.6.1.

As all primary safety endpoint outcomes will be determined based on the 3-month follow-up date per protocol definition of PAEs, all Clinical Events Committee (CEC)-adjudicated PAE cases will be considered final at the 3-Month CSR.

If there are any changes to the PAE data in the final 12-month follow-up data, the data will be summarized descriptively using the mITT and Safety analysis sets and reported in the Final CSR. Descriptive statistics may also be presented for Roll-In analysis set.

7.5.1.1. Primary Effectiveness Endpoint

The primary effectiveness endpoint of acute effectiveness will be evaluated using the exact test for binomial proportion at a one-sided significance level of 2.5%. If the lower bound of the exact two-sided 95% confidence interval of the acute effectiveness success rate is greater than the performance goal of 90%, the study will be considered to have demonstrated effectiveness. The study has met its primary effectiveness endpoint.

The hypothesis testing will be performed in the PP analysis set. Subjects with non-missing acute effectiveness outcome data will be included in the primary analysis. Subjects who are discontinued (i.e., no energy delivered with the study catheter/system) due to study device related reasons will be considered acute effectiveness failures, regardless of the PV isolation achieved or not. Subjects who are discontinued due to non-study device related reasons will be considered missing outcomes.

To investigate the robustness of the analysis result, sensitivity analyses including estimation of the acute procedure success rate in the mITT analysis set, worst-case and best-case scenario analyses, and tipping point analysis will be performed in the mITT and PP analysis sets. Details are provided in Section 7.6.2.

As all acute effectiveness endpoint outcomes will be determined on Day 0 (i.e., date of the index procedure), all data will be considered final at the 3-Month CSR. There will be updates made to the primary acute effectiveness descriptively if any changes are present in the Final CSR. Descriptive statistics may be presented for Roll-In subjects.

7.5.2 Criteria for Study Success

The study will be considered a success if both primary safety and acute effectiveness endpoints are met based on the 3-month follow-up data.

7.6 Sensitivity Analyses

The sensitivity analyses will be performed for the primary endpoints based on the 3-month follow-up data.

7.6.1 Primary Safety Endpoint

Sensitivity to Analysis Sets

CCI [Redacted]

Best-Case Scenario

CCI [Redacted]

Worst-Case Scenario

CCI [Redacted]

Tipping Point Analysis

CCI [Redacted]

CCI [Redacted]

7.6.2 Primary Effectiveness Endpoint

Sensitivity to Analysis Sets

CCI [Redacted]

Best-Case Scenario

CCI [Redacted]

Worst-Case Scenario

CCI [Redacted]

Tipping Point Analysis

CCI [Redacted]

7.7 Subgroup Analyses

In order to provide additional characterization and interpretation of the primary endpoints, the following subgroup analyses will be performed. CCI [Redacted]

[Redacted]

- **Baseline Characteristics**
 - Age group: <65 vs. ≥65 years

- Sex: Male vs. Female
- CHA₂DS₂-VASc Score: ≤ 2 vs. > 2

7.8 Handling of Missing Data

7.8.1 Primary Safety Endpoint

CCI [Redacted]

7.8.2 Primary Effectiveness Endpoint

CCI [Redacted]

7.8.3 Secondary Effectiveness Endpoint

CCI [Redacted]

[Redacted]

7.9 Adjustments for Multiplicity

The secondary endpoint will only be tested if both primary endpoints are met CCI C

[Redacted]

[Redacted]

CCI [Redacted]

7.10 Analyses of Secondary Endpoints

If success is achieved in both the primary safety and acute effectiveness endpoints, then the secondary effectiveness will be evaluated using the Kaplan-Meier estimate.

CCI [Redacted]

The testing of the hypothesis for the secondary effectiveness endpoint after the success of the primary endpoints are met ensures family-wise error rate is controlled at a 2.5% level.

The secondary effectiveness endpoint will be tested in the PP analysis set when all subjects have completed their 12-month follow-up. The analyses results will be reported in the final CSR.

The following additional analysis will be performed for the secondary effectiveness endpoint based on 12-month follow-up data:

- **Sensitivity to Analysis Set**

CCI [Redacted]

- **Exact Test for Binomial Proportion Analysis**

CCI [Redacted]

- **Best-case Scenario**

CCI [Redacted]

[Redacted]

CCI

- **Worst-case Scenario**

CCI

7.11 Additional Endpoint Analyses

No formal statistical hypothesis will be formulated and tested for the additional endpoints. Descriptive statistics will be provided on all additional endpoints in the analysis sets specified below.

7.11.1 Additional Procedural Endpoints

The following procedural data will be summarized descriptively in the PP, mITT, and Roll-In analysis sets:

- Total procedure time, PVI time, PF application time and mapping time
- Number of PF applications by left and right PV and by subject
- Total fluoroscopy time
- Total study catheter left atrial dwell time
- Ablation settings used

7.11.2 Additional Safety Endpoints

The following analyses for the additional safety endpoints will be summarized descriptively in Safety, mITT, and Roll-In analysis sets as the total number of events, number of subjects with events, and percentage of subjects with events:

- Occurrence of Serious Adverse Device Effects (SADEs)
- Occurrence of Unanticipated (Serious) Adverse Device Effects (USADEs)

- Occurrence of Serious Adverse Events (SAEs) within 7 days (early-onset), 8-30 days (peri-procedural), and >30 days (late onset) of index ablation procedure
- Occurrence of non-serious adverse events (non-SAEs)

7.11.3 Additional Effectiveness Endpoints

The following analyses for additional effectiveness endpoints will be summarized descriptively in the PP, mITT, and Roll-In analysis sets after all study subjects completed the 12-month follow-up. CCI

- **Single Procedural Success** is defined as freedom from documented symptomatic atrial arrhythmia (AF, AT or AFL of unknown origin*) episodes based on electrocardiographic data (≥ 30 seconds on arrhythmia monitoring device) during the effectiveness evaluation period (Day 91-Day 365) following a single index ablation procedure. Subjects who had repeat procedure(s) for the study arrhythmia post the index procedure will be deemed failures of this endpoint. CCI

- **Freedom from documented symptomatic atrial arrhythmia (AF, AT or AFL of unknown origin*):** Kaplan-Meier estimates and plots will be used to characterize the time to first documented symptomatic atrial arrhythmia (AF, AT or AFL) recurrence based on electrocardiographic data (≥ 30 seconds on arrhythmia monitoring device) during the effectiveness evaluation period (Day 91-Day 365) at 12 months post the index procedure.

[figure not shown]
Acute procedural failure (i.e., failure to confirm entrance block in all PVs except those that are silent and/or cannot be cannulated post-procedure, use of non-study catheter for PV isolation, and failure to have energy delivery with the study device due to ablation system malfunctions) will also be considered a failure.

- **Freedom from documented (symptomatic and asymptomatic) atrial arrhythmia (AF, AT or AFL of unknown origin*) with additional failure models:** Kaplan-Meier estimates and plots will be used to characterize the time to first documented (symptomatic and asymptomatic) atrial arrhythmia (AF, AT or AFL) based on electrocardiographic data (≥ 30 seconds on arrhythmia monitoring device) during the effectiveness evaluation period (Day 91-Day 365).

The event-free rate will also be summarized descriptively as the number and percent of subjects free from documented (symptomatic and asymptomatic) atrial arrhythmia (AF, AT or AFL) during the evaluation period. The following criteria will also be deemed failures:

- Failure to achieve acute procedural success.
 - Taking a new Antiarrhythmic Drug (AAD) (Class I / Class III) for atrial tachyarrhythmia (AF, AT or AFL of unknown origin*) or taking a previously failed Class I/III AAD at a greater than the highest ineffective historical dose for AF/AFL/AT during the effectiveness evaluation period (Day 105 – Day 365).
 - Greater than 1 repeat ablation for AF/AT or AFL of unknown origin* in the blanking period or any repeat ablation for AF/AT or AFL of unknown origin* during the effectiveness evaluation period.
- **Use of a non-study device** for the purpose of PVI (i.e., touch-up) among all clinically relevant targeted PVs. The number and percentage of subjects and number and percent of clinically relevant PVs ablated by a non-study catheter (NSC) for PVI will be summarized.

CCI

- **Acute reconnection** identified by adenosine/isoproterenol challenge among all clinically relevant targeted PVs.

CCI

CCI

- **Repeat ablation procedures** for left atrial arrhythmia (AF, AT or AFL of unknown origin*) within the 12-month FU period. Procedures for new CTI dependent flutter in the follow up period are not considered repeat procedures per CIP. Following analyses will be performed to delineate the repeat ablation procedure.

CCI

CCI

[figure not shown]
- **Quality of Life (QoL)** is defined as the change of QoL assessed by comparing the Atrial Fibrillation Effect on Quality-of-Life (AFEQT™) scores before and at 3, 6 and 12- months after the ablation procedure.

CCI

The AFEQT questionnaire will only be used in countries with validated languages. These analyses will be conducted for subjects in countries where the AFEQT questionnaires are applied.

- **Hospitalization for cardiovascular events** through 12 months follow-up compared to 12 months prior to baseline. CCI

CCI

7.12 Subset Analyses

The same subjects will participate in all four (4) subsets, which include a PVI Durability subset, a Neurological Assessment (NA) subset, a Cardiac Computed Tomography (CT) or Magnetic Resonance Angiogram (MRA) image subset and an Esophageal Endoscopy (EE) subset.

The subset analysis will be summarized in individual subset independently after all study subjects completed the 3-month follow-up. Additionally, the subset analysis will be performed again after all study subjects completed the 12-month follow-up if there are any updates after 3-month follow-up and data was presented in the 3-month CSR previously.

7.12.1 Analysis of PVI Durability Endpoint

The percentage of targeted PVs in the index ablation procedure being durably isolated evidenced by confirmation of isolation via electroanatomical mapping 75 days (+/- 15 days) post index ablation procedure.

[figure not shown]
Percentage of subjects with durably isolated targeted PVs, evidenced by confirmation of isolation via electroanatomical mapping at 75 days (+/- 15 days) post index ablation procedure.

These analyses will be performed in the PVI Durability analysis set.

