## **7 Study design and Endpoints**

### **7.1 Description of the Study Design**

The study will be carried out as an interventional, prospective, multicenter, single-arm safety and effectiveness evaluation using the OMNYPULSE™ Bi-Directional Catheter in conjunction with the guiding sheath and the TRUPULSE™ Generator.

The study will enroll subjects with symptomatic PAF who are candidates for catheter ablation. Subjects who sign the Informed Consent Form (ICF) and who meet all eligibility criteria will be enrolled and treated with the OMNYPULSE™ Catheter and the TRUPULSE™ Generator.

The first two subjects for each ablating physician will be considered a roll-in subject to verify consistent workflow of study device components and to minimize any learning curve effects. The roll-in phase will include up to 50 subjects. A maximum sample size of 135 evaluable subjects is planned in the main study. All study subjects will be followed-up for 12 months after study procedure.

For the purpose of characterization of safety and to provide an assessment of lesion durability of the investigational ablation system, four (4) subsets will be embedded in the main study; the Neurological Assessment (NA), a Cardiac Computed Tomography (CT) or Magnetic Resonance Angiogram (MRA) imaging (CT/MRA), an Esophageal Endoscopy evaluation (EE) and a PVI durability subset in a prospective manner. Each subset will consist of the same 30 subjects, who will undergo the index ablation procedure and additional neurological, PV, esophageal and PVI durability assessments. The same subjects will participate in all four (4) subsets.

All subjects will be evaluated prior to the procedure, prior to discharge, and post procedure at 7 days (day 7-9), 1 month (day 23-37), 3 months (day 76-104), 6 months (day 166-194), and 12 months (day 335-379).

Planned statistical analyses of the endpoints and analysis populations are described in the Statistical Analysis section (section 19) of this clinical investigational plan and in the Statistical Analysis Plan (SAP). The results for the roll-in phase will be analyzed and presented separately from the main study phase.

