### 7.3.4 PVI Durability Subset

A subset of 30 study subjects will be enrolled in the PVI durability subset and will, in addition to the index ablation procedure and general follow-up schedule, undergo an electro-anatomical re-map procedure at 75 days (+/- 15 days) post index ablation procedure. The re-map is intended to evaluate the durability of the pulmonary vein isolation generated at the index ablation procedure. The assessment of lesion durability will be done by the physician at the participating sites.

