### **7.4.3 Additional Effectiveness Endpoints**

**PVI Durability (for PVI Durability subset):** defined as a sustained isolations of PVs that are targeted in the index ablation procedure, which is evidenced by the confirmation of isolation via the electroanatomical mapping 75 days (+/- 15 days) post index ablation procedure.

**Single Procedural Success:** defined as freedom from documented symptomatic atrial arrhythmia (AF, AT or AFL of unknown origin\*) episodes based on electrocardiographic data ( $\geq 30$  seconds on arrhythmia monitoring device) during the effectiveness evaluation period (day 91-day 365) following a single index ablation procedure.

**Freedom from documented symptomatic atrial arrhythmia** (AF, AT or AFL of unknown origin\*) episodes based on electrocardiographic data ( $\geq 30$  seconds on arrhythmia monitoring device) during the effectiveness evaluation period (day 91-day 365). Acute procedural failure will also be considered failure of 12-month symptomatic recurrence free endpoint.

**Freedom from documented (symptomatic and asymptomatic) atrial arrhythmia** (AF, AT or AFL of unknown origin\*) episodes based on electrocardiographic data ( $\geq 30$  seconds on arrhythmia monitoring device) during the effectiveness evaluation period (day 91-day 365) **with extra failure modes**. A subject who meets any of the following criteria will also be deemed an effectiveness failure:

- Failure to achieve acute procedural success.
- Taking a new Antiarrhythmic Drug (AAD) (Class I / Class III) for atrial tachyarrhythmia (AF, AT or AFL of unknown origin\*) or taking a previously failed Class I/III AAD at a greater than the highest ineffective historical dose for AF/AFL/AT during the effectiveness evaluation period (day of 3-month visit – day 365).
- Greater than 1 repeat ablation for AF/AT or AFL of unknown origin\* in the blanking period or any repeat ablation for AF/AT or AFL of unknown origin\* during the effectiveness evaluation period.

**Use of a non-study device** for the purpose of:

- PVI (i.e., touch-up) among all clinically relevant targeted PVs during index ablation procedure.
- Ablation of left atrial non-PV AF targets (i.e., posterior wall) during index ablation procedure or for repeat procedures during blanking period.

**Acute reconnection** identified by adenosine/isoproterenol challenge among all clinically relevant targeted PVs.

[figure not shown]

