**Figure 5: VISITAG™ settings**

- All subjects will undergo PV ablation with the investigational device until PVI is achieved in all targeted PV's:
  - ONLY after investigator deems unable to achieve PVI with the investigational device, a commercial and compatible BWI (RF) catheter and generator can be used to complete the procedure (PVI only).
- **REQUIRED:** Confirmation of entrance block (exit block is optional) / PVI of all clinically relevant targeted PVs
  - To verify entrance block, analyze electrograms in coronary sinus and/or atrial paced rhythm to confirm that no PV potentials are present.

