#### During the blanking period:

- Repeat procedures during the blanking period ( $\leq 90$  days post index ablation procedure) must be conducted with the investigational device, with or without focal touch-up, if the arrhythmia is due to PV triggers. ONLY after investigator deems unable to achieve PVI with the investigational device, a commercial and compatible BWI (RF) system can be used to complete the procedure (PVI only).
- If the arrhythmia is due to non-PV triggers and the subject is treated with a commercially available ablation catheter and generator, the subject will be excluded from the long-term effectiveness cohort.
- Procedures for newly CTI dependent flutter in the follow up period are not considered repeat procedures per CIP and will be treated with a commercially available ablation catheter and generator.

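### As legibly worded, the PVI durability rates do not separate veins completed with commercial RF at index or re-ablated before the remap, so they can overstate study-device durability

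*SAP*

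**What the plan says.** **The rates.** SAP 7.12.1 gives the vein-level rate as "The percentage of targeted PVs in the index ablation procedure being durably isolated evidenced by confirmation of isolation via electroanatomical mapping 75 days" and the subject-level rate as "Percentage of subjects with durably isolated targeted PVs, evidenced by confirmation of isolation". It adds that "These analyses will be performed in the PVI Durability analysis set". Protocol 19.8.5 has the same two rates. Protocol 7.4.3 defines the endpoint as "sustained isolations of PVs that are targeted in the index ablation procedure", shown by the remap.

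**The purpose.** Protocol 7.1 says the subset is there "to provide an assessment of lesion durability of the investigational ablation system". Protocol 7.3.4 says: "The re-map is intended to evaluate the durability of the pulmonary vein isolation generated at the index ablation procedure".

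**What may happen to a vein before the remap.**
- At index (protocol 13.3.3, PVI steps): "ONLY after investigator deems unable to achieve PVI with the investigational device, a commercial and compatible BWI (RF) catheter and generator can be used" to finish the isolation.
- In the blanking period, up to day 90 (protocol 13.4), repeat procedures "must be conducted with the investigational device, with or without focal touch-up, if the arrhythmia is due to PV triggers", with RF available if the study device fails. Protocol 13.5 keeps the visit schedule tied to the index procedure after a repeat.

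**The acute endpoint.** Protocol 7.4.1 and SAP 7.4.2 count PVI that needs a non-study device as an acute failure.

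**What cannot be read.** The definition of the PVI Durability analysis set is redacted in protocol 19.3 and SAP 5.1.

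**The concern.** The unit counted is a PV targeted at index, and the test is whether it maps as isolated at day 60 to 90. A vein can meet that test in two ways that are not durable isolation by the study device.

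1. **RF completion at index.** The study device fails to isolate the vein and a commercial RF catheter finishes it. The vein was targeted and, if it stays isolated, it counts as durable. The same case is a device failure on day 0 and a durability success at the remap.
2. **Re-ablation before the remap.** The vein reconnects, is re-isolated at (say) day 40, and maps as isolated at day 75. The index lesion did not last, but a single map at day 75 cannot show that.

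The remap rate is the trial's planned, systematic look at lesion durability. It comes from about 30 subjects and is summarised once all subjects have completed 3-month follow-up (SAP 7.12). A reader of the report would take it as a property of the investigational system, because protocol 7.1 says that is its purpose. Elsewhere the plan does attend to device attribution: protocol 19.8.3 censors subjects when a commercial RF device is used outside the PV region, and SAP 7.5.1.1 scores device-related discontinuations as acute failures whether or not the veins were isolated.

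**Working it through.** The documents give no expected durability rate, goal or precision for this endpoint, so there is no figure to reproduce. The check is a timing comparison followed by a sensitivity calculation.

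**Timing.** Remap window: 75 − 15 = day 60 to 75 + 15 = day 90. Repeat PVI is allowed up to day 90. A repeat can therefore precede the remap. Ablation done at the remap visit (protocol 13.5.2) follows the finding of reconnection, so it does not affect the rate.

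**Inputs.** Subset target 30 (SAP 6). Four PVs per subject is an assumption, giving N = 120 veins. Let k be the number of affected veins (RF-completed or re-ablated), q the share of them isolated at the remap, and r the isolation rate in the other veins.

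- As written: [(N − k)r + kq]/N
- Affected veins excluded: r
- Affected veins counted as not durable: (N − k)r/N

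The gap against the failure rule is kq/N. The gap against exclusion is (k/N)(q − r).

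**Vein level, with q = 1 and whole-vein counts:**

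| k | Other veins isolated | As written | Excluded | Failure | Gap vs excluded | Gap vs failure |
|---|---|---|---|---|---|---|
| 3 | 82/117 | 85/120 = 70.8% | 70.1% | 68.3% | 0.7 | 2.5 |
| 6 | 80/114 | 86/120 = 71.7% | 70.2% | 66.7% | 1.5 | 5.0 |
| 12 | 76/108 | 88/120 = 73.3% | 70.4% | 63.3% | 3.0 | 10.0 |
| 3 | 105/117 | 108/120 = 90.0% | 89.7% | 87.5% | 0.3 | 2.5 |
| 6 | 103/114 | 109/120 = 90.8% | 90.4% | 85.8% | 0.5 | 5.0 |
| 12 | 97/108 | 109/120 = 90.8% | 89.8% | 80.8% | 1.0 | 10.0 |

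Gaps are in percentage points, taken before rounding.

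**Subject level, 21/30 = 70.0% as written, with every affected subject among the 21:**

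| Affected subjects | Excluded | Failure |
|---|---|---|
| 1 | 20/29 = 69.0% | 20/30 = 66.7% |
| 2 | 19/28 = 67.9% | 19/30 = 63.3% |
| 3 | 18/27 = 66.7% | 18/30 = 60.0% |

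Each affected subject moves the rate by up to 1/30 = 3.3 points under a failure rule. For scale, the exact 95% interval for 21/30 is 50.6% to 85.3%.

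**How likely is any affected subject?** The documents give no rate. If 2%, 5% or 10% of subjects are affected (assumed), the chance of at least one in 30 is 1 − 0.98^30 = 45%, 1 − 0.95^30 = 79% or 1 − 0.90^30 = 96%.

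**The case against.** **The analysis set is redacted.** A reader might infer that RF-completed and re-ablated veins will be credited as durable. The documents do not support that as fact. If the hidden set leaves out subjects with non-study-device PVI or an early repeat, all their veins drop from numerator and denominator and the problem goes. This stands, and it is why the point is conditional. It does not remove the need for clarity, because exclusion and failure give different answers (66.7% against 60.0% in the example with 3 subjects).

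**The wording already excludes re-ablated veins.** Protocol 7.4.3 asks for *sustained* isolation and 7.3.4 refers to the isolation made at index. Both lean against credit for a vein that reconnected. This partly stands. However, 7.4.3 also makes the remap the evidence, and one map cannot reveal an earlier reconnection. The wording does not touch the RF route, where the isolation may well be sustained.

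**The bias need not be upward.** A reader might infer that both routes can only inflate the rate. That is true only against a failure rule. Against exclusion the gap is (k/N)(q − r), which is negative if affected veins do worse than the rest.

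**A larger figure is tempting but weak.** The acute test can pass with 6 failures in 135 (129/135 has an exact lower bound of 90.58%; 128/135 has 89.6%), or 6 × 30/135 = 1.3 per 30 subjects. Adding an assumed 3% to 10% repeat rate (0.9 to 3 subjects) gives about 2.2 to 4.3 subjects, or 7 to 14 points. This stacks the worst passing acute result on a repeat rate with no source in the documents, and needs every affected subject to map as fully isolated. Acute failures also include discontinued subjects, who skip the remap (protocol 19.5).

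**Related data are reported elsewhere.** Non-study-device PVI, repeat ablation and PV reconnection at repeat procedures are summarised separately (protocol 19.8.5, SAP 7.11.3). A careful reader could see how often the issue arose, but not a corrected durability rate.

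**Conclusion.** The point holds in conditional form. On the legible wording, the durability rates measure whether targeted veins are isolated at the remap, without regard to device or re-treatment. Unless the redacted analysis set deals with it, they can overstate the durability of index isolation by the investigational system. This is clear for RF-completed veins and arguable for re-ablated ones.

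The size rests on assumed counts: 4 PVs per subject, 3 to 12 affected veins or 1 to 3 affected subjects, and all of them isolated at the remap. Choosing between failure and exclusion is a judgement. A vein the study device never isolated has no study-device durability to measure, so exclusion is defensible, and its acute failure is already counted elsewhere.

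The endpoint carries no hypothesis (protocol 19.8.5), and success depends only on the two primary endpoints (SAP 7.5.2). The consequence is a durability figure that may be misread, not a changed trial conclusion. It is worth fixing because the remedy is cheap.

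**What to change.** In SAP 7.12.1 and protocol 7.4.3 and 19.8.5:

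1. Add a vein-level rule. The study-device durability rate credits a targeted PV only if it was isolated at index with the study device alone, was not re-ablated before the remap, and is isolated at the remap.
2. Report beside it the rate for targeted PVs isolated at the remap by any means. Give both rates at vein and subject level.
3. State whether affected PVs count as not durable or are excluded, and what one affected PV does to the subject-level result. Show both versions, with the number of affected veins and subjects.
4. If the redacted PVI Durability analysis set already removes these cases, say so in SAP 7.12.1.

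The cost is wording and a few table rows. The data are already planned: SAP 7.11.3 summarises PVs ablated with a non-study catheter, and protocol 13.4 and 19.8.5 cover repeat procedures and reconnection by index-treated PV. The reported rate may be slightly less favourable.
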